| PHI | Protected health information |
| PI | Principal Investigator |
| PR | Partial response |
| RWJUH | Robert Wood Johnson University Hospital |
| SAE | Serious adverse event |
| SCC | Squamous Cell Carcinoma |
| SD | Stable disease |
| SGOT | Serum glutamic oxaloacetic transaminase |
| SGPT | Serum glutamic pyruvic transaminase |
| ULN | Upper limit of normal |

1. Purpose/Specific Objectives

The purpose of this protocol is to serve as a pilot study for neoadjuvant cetuximab in advanced head and neck SCC. The primary hypothesis is that patients who are selected by response to neoadjuvant cetuximab and go on to receive concurrent cetuximab RT will have improved 2 yr locoregional control compared to unselected patients who receive cetuximab RT. The overall treatment strategy expressed in the protocol is to treat stage III/IV head and neck SCC patients (oropharynx, larynx, hypopharynx) with 3 weeks of neoadjuvant cetuximab, select those patients who respond (develop cetuximab related folliculitis or at least a partial response by CT RECIST 1.1 criteria) and then treat them with concurrent external beam radiation therapy (EBRT) and cetuximab. Those patients who do not respond will receive concurrent cisplatin and EBRT. The hope is that the data derived from this study will lead to a large phase II or phase III trial.

1.1 Primary Endpoint

The primary endpoint is 2 yr locoregional control in cetuximab responders. Our hypothesis is that patients who respond to neoadjuvant cetuximab and go on to receive concurrent cetuximab RT will have improved 2 yr locoregional control compared to unselected patients who receive cetuximab RT ie the cetuximab RT arm in the seminal Bonner randomized trial. The Bonner trial randomized advanced HNSCC to RT alone versus cetuximab RT.¹ The patients in the cetuximab arm were completely unselected, and had a 2 yr LRC of 50%. In the update, he noted that of the cetuximab treated patients, development of a significant rash (folliculitis) had a huge prognostic impact, with significant rash patients having a OS more than twice as long as no significant rash patients (68.8 months vs 25.6 months; HR 0.49, 0.34–0.72; p=0.002).²

Our hypothesis is that if patients are selected by response to neoadjuvant cetuximab, that those patients will have at least a 25% improved LRC over those historical cetuximab patients who were unselected. Given the difference that rash appears to make, we feel this is a very reasonable estimate.

1.2 Secondary Endpoint(s)

1.2.1 Assess secondary clinical endpoints such as the percent of patients receiving neoadjuvant cetuximab who progress by CT RECIST 1.1 criteria during the neoadjuvant cetuximab. All patients in the protocol will receive a CT with IV contrast prior and also after neoadjuvant cetuximab. Progression will be gauged using the RECIST 1.1 CT criteria for progression (at least a 20% increase in the sum of the LD of target lesions, taking as reference the pre-cetuximab scan or the appearance of one or more new lesions). If it is found that the prior probability that 20% or more of the patients are progressing during neoadjuvant cetuximab is at least 90%, the protocol will be stopped (section 16.8). The first interim analysis will be performed after 12 patients. We will also assess the 2 yr locoregional control for non-responders to neoadjuvant cetuximab. We will also assess the complete response rate to PET/CT scan 3 months after the completion of radiation therapy for both responders and for

non-responders to neoadjuvant cetuximab, as PET/CT has a NPV of 95% in this setting, so will give a very good indication of eventual locoregional control.³

1.2.2 Molecular correlates. All patients must have a biopsy of the locoregional disease (primary site or neck lymph nodes), and of the skin prior to therapy. When feasible, patients will also have another biopsy of the locoregional disease and skin after 3 weeks of neoadjuvant cetuximab but prior to starting radiation therapy. If there is a locoregional recurrence, a third biopsy of locoregional disease is possible. The second biopsy after neoadjuvant cetuximab and third biopsy in case of recurrence are strongly recommended but not absolutely necessary for participation in the protocol. Therefore, this protocol offers a unique chance to investigate molecular correlates because 1) the neoadjuvant therapy is a single agent, as opposed to a chemotherapy cocktail (and so the change in protein production is due to a single agent as well), 2) we will obtain normal tissue (skin) samples and tumor samples from before and after 3 weeks of cetuximab, so we will have in-vivo tissue to analyze after this single agent.

Our goals in the molecular analysis are to explore the following possibilities:

1. Analyze the relationship of known DNA mutations in tumor per the FoundationOne™ (or other certified genomic analysis facility) genomic profile, and correlate to clinical endpoints such as locoregional control.
2. Analyze any changes in protein production at the tumor in response to 3 weeks of cetuximab i.e., does the tumor attempt to bypass the effect of EGFR inhibitor by a) accelerating protein production downstream of EGFR receptor or b) transferring dependence to a completely different pathway from EGFR such as IGF-1R?
3. Analyze any changes in protein production at the skin in response to 3 weeks of cetuximab? Are there markers in the skin that might indicate susceptibility to develop folliculitis during cetuximab? Or do they shed light on the strong relationship between folliculitis and efficacy of cetuximab?

Molecular investigations include: 1) Genomic testing of tumor DNA using the FoundationOne™ (or other certified genomic analysis facility) genomic profile from paraffin embedded tumor samples taken before cetuximab or after locoregional/distant failure 2) RNA sequencing of tumor and skin samples from before and after cetuximab, 3) IHC analysis of EGFR downstream pathways. Of these, the first priority will be genomic testing per the FoundationOne assay, as this will be funded by the Cancer Institute of New Jersey Precision Medicine. As funds from grants or the radiation oncology department become available, the other molecular investigations may be completed.

These secondary molecular endpoints are observational, as there is very minimal data available regarding any of these questions. The study will not be powered for these molecular endpoints.

1.2.3 Image correlates: In the current protocol, the role of CT or PET/CT is to provide treatment planning and response assessment during the course of the treatment. All patients will have PET/CT imaging prior to the treatment, and after 3 months of all the treatment. There will also be CT neck with IV contrast after 3 weeks of neoadjuvant cetuximab but prior to radiation therapy. With this full panel of image set, the current protocol would allow for further study to investigate

whether the tumor imaging characteristics including anatomical and molecular parameters evaluated by PET/CT, either alone or combined with other biomarkers can attribute to the better prediction for the clinical outcomes, as 1) the response to neoadjuvant cetuximab; and 2) the final clinical endpoint, the 2-year local regional controls.

As quantification of both baseline variability and intra-treatment change is necessary to optimally incorporate functional imaging into adaptive therapy strategies, in this protocol all the image characteristics will be analyzed quantitatively. The volume, surface area and the longest diameter of the lesion will be measured based on anatomic CT image. The standard uptake value (SUV) from PET activity will be analyzed using on both region-of-interest (ROI) basis and voxel-by-voxel basis after fusing with CT. Maximum standardized uptake value (SUVmax), the peak SUV (SUVpeak within a 1cm³ sphere centered on SUVmax), the total SUV (SUVtotal, sum of SUV value of every voxel within the tumor region), the mean SUV within the outlined tumor region (SUVmean), the metabolic tumor volume (MTV) using 40% SUVmax as threshold and the total lesion glycolysis (TLG), from the pre-treatment PET will be calculated. Also the ¹⁸F-FDG PET based tumor proliferation response (after neoadjuvant cetuximab and after the whole course of treatment) will be quantified by the change in each SUV measure relative to baseline. Univariate and multivariate analysis will be performed to identify whether imaging variables alone or combined with the clinicopathological, genomic profile, as well as the regimen choice can associate with clinical outcomes as the response to the neoadjuvant cetuximab and the response to the cocktail of the treatment. As these investigations are observational based on the amount of data will be finally collected and no power analysis is performed for this part.

2. Background and Significance

For many advanced (stage III/IV) HNSCC, the standard of care is EBRT and concurrent systemic therapy, typically either cisplatin or cetuximab. There is ample evidence to justify either one as concurrent therapy. The MACH NC meta-analysis demonstrated a 5 year overall survival advantage of 6.5% for concurrent chemotherapy. When monochemotherapy was given, cisplatin was superior to other chemotherapy.⁴ In addition, randomized trials have demonstrated a locoregional control benefit to adding cisplatin based chemotherapy to EBRT in advanced HNSCC⁵ as well as advanced laryngeal cancer.⁶

Cetuximab is a monoclonal antibody to EGFR (epidermal growth factor receptor) that is used in combination with radiation therapy for advanced HNSCC and in combination with chemotherapy for recurrent or metastatic HNSCC. Its mechanism of action is likely dual, in that 1) it is a competitive inhibitor of natural EGFR ligands and thus prevents EGFR phosphorylation and 2) elicits ADCC (antibody-dependent cell cytotoxicity).^{7,8} There is even evidence that the response to cetuximab may depend in part on polymorphisms in the Fc receptor on various immune effector cells⁹ In combination with radiation, cetuximab may act as a sensitizer by inhibiting DNA-PK activity, thereby inhibiting double strand DNA repair.¹⁰ A randomized controlled trial by Bonner et al in advanced oropharynx, hypopharynx and larynx SCC of EBRT + cetuximab versus EBRT alone revealed an improvement in 5 year overall survival for the cetuximab arm from 36.4% to 45.6%.¹¹

For many patients, the choice of whether to choose concurrent cisplatin or cetuximab comes down to side effects. Cisplatin potentiates the radiation reaction, and therefore skin reaction and mucositis is clearly worse with the combination of cisplatin and EBRT than EBRT alone. In addition, cisplatin can also markedly decrease blood counts and cause significant nausea and vomiting. This toxicity is often severe, requiring hospitalization for pain control, IV hydration and often PEG tube insertion. On the other hand, cetuximab does not potentiate the radiation toxicities, so the rates of grade 3 mucositis and anorexia are similar to that for EBRT alone. Cetuximab does often cause a rash that is usually well managed with antibiotics, and actually correlates to improved effectiveness of cetuximab in rash positive patients. Therefore, older patients and patients with worse performance status often receive EBRT and cetuximab rather than cisplatin, for its milder toxicity profile.

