Clinical activities will take place at Rutgers New Jersey Medical School in Newark and Rutgers Cancer Institute of New Jersey. Some molecular correlative studies will be performed at Rutgers Cancer Institute of New Jersey.

4. Experimental Design and Methods

*if tooth extraction is necessary, should be extracted during neoadjuvant cetuximab or before so as not to delay radiation therapy. All patients will be encouraged to have PEG placed prior to radiation or early on in the radiation course but failure to do so will not exclude them from the protocol.

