7.2 Sequence of treatment

7.2.1 Prior to neoadjuvant cetuximab

Patients will be staged using PET/CT to delineate the extent of disease. Preferably, they would receive PET/CT with IV contrast so that the CT may be used to assess response to cetuximab (CT without IV contrast is not adequate for assessing the tumor or lymph nodes). In case the staging PET/CT has already been done, a CT neck with IV contrast will be ordered prior to receiving neoadjuvant cetuximab, so that the RECIST 1.1 criteria may later be applied. In case the patient cannot receive PET/CT due to insurance issues, CT neck and chest with IV contrast may be substituted.

Initial biopsy specimen (incisional/core biopsy as opposed to a FNA) will be procured from the head and neck (primary site) and punch biopsy obtained from the skin. As tissue from

the head and neck and skin will be used for DNA and RNA genotyping, tissue that is preserved and sufficient in quantity is required. So even if a patient has had a previous biopsy that is paraffin encased, a repeat biopsy may be obtained. These specimens will be handled as delineated in section 11.3.

All patients will be referred for dental evaluation. If any dental extractions are required, they should be performed early in the course (1st week preferably) of neoadjuvant cetuximab, so that radiation therapy is not delayed. Patients may be referred for PEG if appropriate. PEG should be placed during the course of neoadjuvant cetuximab or early in the course of radiation therapy, so that there is minimal esophageal mucositis at the time of PEG placement.

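### SUVtotal is an unweighted sum over voxels, so it is comparable between PET scans only if voxel size is constant or corrected for, which the protocol does not require

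*Combined protocol and SAP*

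**What the plan says.** The imaging correlates are set out in Section 1.2.3 of the combined protocol and SAP. PET uptake "will be analyzed using on both region-of-interest (ROI) basis and voxel-by-voxel basis after fusing with CT". The list of measures includes SUVmax, SUVpeak, SUVmean and "the total SUV (SUVtotal, sum of SUV value of every voxel within the tumor region". It ends with "the metabolic tumor volume (MTV) using 40% SUVmax as threshold and the total lesion glycolysis (TLG), from the pre-treatment PET will be calculated". No formula is given for TLG.

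The measures are used in two ways:

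- **Within a patient.** PET response "will be quantified by the change in each SUV measure relative to baseline". Whether that change is absolute or relative is not stated.
- **Between patients.** "Univariate and multivariate analysis will be performed to identify whether imaging variables alone or combined with the clinicopathological, genomic profile" are associated with response and outcome.

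The section describes the work as observational and says that "no power analysis is performed for this part".

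On where the scans come from, Section 3 states: "Clinical activities will take place at Rutgers New Jersey Medical School in Newark and Rutgers Cancer Institute of New Jersey". Section 15 says that both institutions enrol, while Section 5.5 names only Newark as a source of recruitment. Section 6 accepts a baseline PET/CT up to 2 months old at enrollment and schedules the next one 3 months after radiation, give or take a month. Section 7.2.1 provides for a scan that pre-dates entry: "In case the staging PET/CT has already been done, a CT neck with IV contrast will be ordered". None of these sections names a scanner, a reconstruction, a voxel size or a common grid for PET.

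**The concern.** A sum over voxels counts voxels as well as uptake. Divide the same tumour into smaller voxels and there are more terms to add, so the total rises although nothing in the patient has changed. SUVmean does not behave this way, because the voxel count cancels.

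This matters for both planned uses. In the between-patient models, part of the spread in SUVtotal could reflect image format rather than tumour burden. In the change from baseline, a patient whose two scans were reconstructed on different grids would show an apparent response, or an apparent increase, caused by the grid. With 27 patients planned (Section 16.2), a few scans on a different grid could dominate the variable.

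**Working it through.** The plan states no numerical value for SUVtotal, so there is no figure to reproduce. The check is algebra, followed by an illustration on assumed values.

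**Inputs from the document:** the unweighted definition in Section 1.2.3; no voxel size anywhere.

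**Inputs assumed:** all voxel dimensions below, and a 20 cm³ spherical lesion whose SUV falls smoothly from a peak of 12 at the centre.

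**Step 1, the formula.** Let V be the region volume, v the voxel volume and n = V / v the number of voxels.

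SUVtotal = Σ SUVᵢ = n × SUVmean = SUVmean × V / v

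SUVmean and V belong to the tumour, and v belongs to the image. Halving v doubles SUVtotal.

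**Step 2, size between two scans of an identical tumour.** The ratio is the inverse ratio of voxel volumes.

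- 3 mm against 5 mm cubes: 5³ / 3³ = 125 / 27 = 4.63
- 2 mm against 4 mm cubes: 4³ / 2³ = 64 / 8 = 8
- Equal voxels: ratio 1, no effect

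**Step 3, change from baseline.** The ratio of follow-up to baseline SUVtotal is the true ratio of SUVmean × V, multiplied by v(baseline) / v(follow-up). If both scans share v, the factor is 1 and a ratio is unaffected. An absolute difference still carries 1/v, so it stays non-comparable between patients with different v. For a tumour that has not changed, 3 mm cubes at baseline and 5 mm cubes at follow-up give 27 / 125 = 0.216, an apparent fall of 78.4%. The reverse order gives an apparent 4.63-fold rise.

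**Step 4, numerical check.** The assumed lesion was sampled on seven grids:

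| Voxel (mm) | v (cm³) | Voxels | Plain sum | SUVmean | Sum × v (SUV × cm³) |
|---|---|---|---|---|---|
| 2 × 2 × 2 | 0.008 | 2511 | 17857 | 7.11 | 142.9 |
| 2 × 2 × 3 | 0.012 | 1667 | 11869 | 7.12 | 142.4 |
| 2.7 × 2.7 × 3.3 | 0.0241 | 835 | 5939 | 7.11 | 142.9 |
| 4 × 4 × 3 | 0.048 | 419 | 2980 | 7.11 | 143.0 |
| 4 × 4 × 4 | 0.064 | 308 | 2203 | 7.15 | 141.0 |
| 4 × 4 × 5 | 0.080 | 249 | 1775 | 7.13 | 142.0 |
| 5.5 × 5.5 × 3.3 | 0.0998 | 213 | 1490 | 7.00 | 148.7 |

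Over the first six grids the plain sum varies 17857 / 1775 = 10.1-fold, while sum × v stays between 141.0 and 143.0 (143.0 / 141.0 = 1.014, about 1.4%). The 2 mm against 4 mm comparison gives 17857 / 2203 = 8.1, in line with the theoretical 8. On the coarsest grid sum × v is 148.7, which is 148.7 / 142.9 = 1.04 times the finest-grid value. There the whole-voxel outline gives a volume of 21.26 cm³ instead of 20, so a small edge effect remains after the correction.

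The check isolates voxel counting. It does not model differences in resolution or noise between scanners, which would affect every SUV measure.

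**The case against.** The strongest reply is that no harm is shown. The document gives no voxel sizes, does not say that PET is done on more than one scanner, and does not rule out resampling to a common grid. Fusion with CT might involve resampling. Most patients are expected from Newark (Section 17.2). Imaging measures appear in neither the outcome list (Section 16.4) nor the analysis list (Section 16.5), and SUVmean, MTV, TLG and CT volume are planned alongside. Anyone holding the images could correct the sum later with one multiplication.

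Much of that stands, and it limits the point. Three stronger readings are tempting, and the document supports none of them:

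- **That SUVtotal cannot be compared across the two sites.** Site is the wrong unit. Two sites with equal voxels cause no difficulty, and two reconstructions at one site do. Section 3 says nothing about PET scanners.
- **That associations with SUVtotal will reflect scanner or referral route.** Section 7.2.1 allows for a staging scan already done. It does not say that the scan was done elsewhere or on other equipment. The document supports could, not will.
- **That TLG already supplies the same quantity on a comparable scale.** SUVtotal is tied to the tumour region. TLG is listed next to an MTV with a threshold of 40% of SUVmax, and its formula is not written. The two coincide, after scaling by voxel volume, only if the region is the same.

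The reply does not remove the defect in the definition. Fusion with CT does not settle the grid, because no CT grid is fixed either: for the response CT, slice thickness is only recommended to be at most 5 mm (Sections 7.2.3.2 and 9.2). A formula followed as written should give the same number for the same tumour, and this one does so only under a condition that the plan never imposes.

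**Conclusion.** The point holds in a conditional form. As defined, SUVtotal varies as 1/v. It is comparable between patients and between time points only if all PET scans share one voxel size, are resampled to a common grid, or are corrected for voxel volume. The document requires none of these.

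The size of the effect in this trial cannot be known from the document. The 4.6-fold and 8-fold figures show what the assumed voxel sizes would do; they are not estimates for these scans, and the effect is nil if voxel size is constant.

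The importance is low. SUVtotal is one of several exploratory, unpowered imaging measures. The primary endpoint, sample size, treatment assignment and stopping rule do not depend on it. It is worth correcting because a better definition costs nothing.

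**What to change.** In Section 1.2.3, define SUVtotal as the sum of voxel SUVs multiplied by voxel volume, in SUV × mL, over the outlined tumour region (equivalently, SUVmean × region volume). Apply that definition at every PET time point, and state whether change from baseline is absolute or relative. Naming one fixed grid to which all PET images are resampled would also make the plain sum comparable.

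If SUVtotal is dropped in favour of TLG, first write out the TLG formula and its region. The substitution is like-for-like only if TLG is computed over the same region as SUVtotal.

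The cost is one line in the imaging section and use of the voxel dimensions of each scan. No new scans, visits or patients are needed. The change does not harmonise PET acquisition in other respects; it removes only the dependence on voxel size.

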2.1 Supporting Data and Rationale

Is Cisplatin RT or cetuximab RT better? Clearly, treating with concurrent cetuximab and EBRT is less toxic than with concurrent cisplatin, but is it as effective? The data are conflicting. The University of Alabama recently compared 29 patients treated with cetuximab EBRT to 103 patients treated with chemotherapy EBRT. All patients were stage III to IVB. At 3 years the locoregional control was not significantly different at 70% for cetuximab and 74% for chemotherapy.¹² On the other hand, MSKCC reported on 49 patients treated with cetuximab EBRT and 125 patients treated with cisplatin EBRT. They found that the 2 year locoregional failure was 5.7% for the cisplatin cohort versus 39.9% for the cetuximab patients. There were several differences in the studies, the most important being that in the MSKCC study, the cetuximab patients were typically older (40.8% cetuximab group versus 5.6% cisplatin group who were 71 yrs old or over) and with worse KPS performance status (40.8% cetuximab group versus 30.4% cisplatin group were KPS 60-80). Most of the Alabama patients were treated on protocol, so unlike what typically happens in the community, the median KPS for the cetuximab patients was actually higher than the cisplatin patients (median KPS of 90 compared to 80). In addition, the MSKCC study only used monotherapy with cisplatin q3 weeks whereas the Alabama study used various chemotherapy regimens. The MSKCC used all IMRT (intensity modulated radiation therapy) versus conventional EBRT in the Alabama study.

Interpreting these conflicting results is difficult. Was the worse locoregional control seen in the MSKCC study due to selecting out older patients with worse performance status? Or is cisplatin truly superior to cetuximab? The RTOG is planning to perform a randomized controlled trial of cetuximab EBRT versus cisplatin EBRT in the future in HPV +, non smokers, but results from this trial will not be available for many years, and will not necessarily apply to HPV(-) patients or to smokers (which is the majority of patients seen at Rutgers New Jersey Medical School - Newark, who are mostly black or Hispanic). To our knowledge, no one has performed a study to assess response to neoadjuvant cetuximab and treating with either cetuximab or cisplatin according to that response.

Is combining cisplatin, cetuximab RT (trimodality therapy) better than cisplatin RT? RTOG 0522 looked at this exact question in patients with stage III-IV carcinoma of the oropharynx, larynx, and hypopharynx received The experimental regimen (Arm A) consisted of

a loading dose and 6-7 weekly doses of cetuximab given in conjunction with the control arm (B) of 70-72 Gy (6 weeks) + 2 cycles of cisplatin (q3 weeks). At 2.4 years, there were no significant differences in progression-free survival (HR [A/B]: 1.05, 0.84-1.29; $P=0.66$; 2-Y rates: 63% vs. 64%), the primary endpoint, or in overall survival (HR: 0.87, 0.66-1.15; $P=0.17$; 2-Y rates: 83% vs. 80%). Though only out in abstract form, as HNSCC recurrences usually occur early, this is almost certainly going to be a negative trial. Therefore, there is no rationale at this point for attempting a protocol using trimodality therapy. Per personal communication with [name] (PI of RTOG 0522), he thinks that the reason that this was a negative trial was that both cisplatin and cetuximab have the same mechanism of action: disabling of DNA repair pathways after radiation.

Determining who will respond to cetuximab on a molecular basis has been extremely difficult. Despite EGFR overexpression in up to 90% of HNSCCs, response to EGFR monotherapy has been modest.¹³ In the EXTREME trial, which randomized patients with metastatic/recurrent head and neck SCC to chemotherapy versus cetuximab + chemotherapy, they noted no clear correlation between level of EGFR receptor level as determined by immunohistochemistry and response to cetuximab.¹⁴ Notably, in the seminal Bonner trial, EGFR receptor status was not mandatory and patients were not stratified by receptor status. Nor is there a relatively simple molecular prognostic indicator of response to cetuximab, such as lack of Kras in colorectal cancer. The mutations and alternate pathways that are theorized to possibly contribute to the resistance to EGFR antagonists are numerous, including mutations in the extracellular and intracellular EGFR, K-ras and H-ras, mutations in Epithelial-mesenchymal transition such as increased vimentin expression, decreased E-Cadherin expression, decreased Claudins 4 and 7 expression, alternate pathways such as Cyclin D1 upregulation, PTEN mutations, PI3KCA mutations, Akt Amplification.¹⁵ One relatively promising target may be EGFR variant III (EGFRVIII), which occurs in 42% of HNSCC and occurs alongside EGFRwt. Due to deletion of amino acids 6–273 of the EGFRwt extracellular domain, EGFRVIII has a truncated ligand binding site and does not bind ligand or cetuximab well. In addition, it has persistent activation of tyrosine kinase ie does not need a ligand to dimerize, and operates only via PI3k pathway (not MEK/Erk like EGFRwt). EGFRVIII is associated w increased proliferation, tumor growth and chemoresistance to anti-tumor drugs including cetuximab. Currently, phase 1 studies of immunotoxin MR1-1 targeting EGFRVIII for CNS tumors are in progress at Duke.

Currently, the picture as to what molecular marker (or more likely, combination of markers) to use to predict responsiveness to EGFR receptors is extremely confusing and complicated. As there is no clear molecular correlate to predict response to cetuximab, we chose to use a clinical response in this protocol. Below are two graphic representations of the EGFR pathway and mechanisms that may either render EGFR inhibitors ineffective or provide an alternate (downstream) mechanism to active this pathway.


[figure not shown]

Fig. 1. EGFR signaling pathway and several mechanisms of resistance to EGFR-targeted therapies.

[figure not shown]

Fig 1. Possible resistance to epidermal growth factor receptor (EGFR) inhibition in head and neck squamous cell carcinoma (HNSCC) as a result of EGFR-independent activation of oncogenes. In addition to oncogenic pathways activated by EGFR, EGFR-independent oncogenesis in HNSCC may result from activation of G protein-coupled receptors (GPCRs), other growth factor receptors, genetic aberrations such as mutation and amplification of oncogenes, loss of tumor suppressor genes, and vascular endothelial growth factor (VEGF) overexpression promoting angiogenesis. MMP, matrix metalloproteinase; IGF-1R, insulin-like growth factor-1 receptor; VEGFR, VEGF receptor; PKC, protein kinase; STAT, signal transducer and activator of transcription; Rb, retinoblastoma.

What role does HPV status have on response to cetuximab?

HPV+ status has recently been shown to have a more favorable prognosis compared to HPV- patients.¹⁶ However, it is not clear how HPV status affects response to cetuximab (note that in the seminal Bonner RCT, they did not check for HPV status, and as of yet, there is no evidence regarding how HPV status affects response to cetuximab). Since HPV+ patients clearly fare better

than HPV- patients, there is much conjecture that HPV+ patients may undergo de-escalation of therapy. However, at this point, there is no data to show that this is safe, and note that outside of this protocol in the community, most HPV+ patients would be treated with cisplatin RT. This protocol potentially offers a rational paradigm for de-escalation of therapy, which would be ideal for the HPV+ patient. Therefore, both HPV+ and – patients are included in this protocol. HPV status is easily obtainable from RNA sequencing, so will be known for each patient.

Rash as a predictor or response to EGFR inhibitors. The only consistent indicator of how a patient will respond to EGFR inhibitors is development of rash. Below is just a sampling of evidence for a better prognosis with significant rash in response to EGFR inhibitors. What is apparent is that there is overwhelming evidence of improved prognosis in patients who develop a rash, and that this effect is consistent over different types of tumors and across different EGFR antagonists.

| Author | Type of cancer | Agent | Results | Notes |
|--------------------------------------|------------------------------|-----------|--|--|
| Bonner ¹⁷ | HNSCC | cetuximab | Grade 2-4 rash had an OS of 68 months compared to 25 months for patients with a Grade 0/1 rash ($p=0.002$). | Of 208 patients receiving cetuximab and having information about rash, 174 (84%) had rash, 127 (61%) had prominent rash, and 81 (39%) had mild to no rash. Furthermore, the majority of the rash developed quickly, roughly 75% occurring in the first 2-3 weeks |
| Perez Soler Montefiore ¹⁸ | NSCLC, HNSCC, ovarian | Erlotinib | For NSCLC, patients with no rash, grade 1 rash and grade 2/3 rash had OS of 46 days, 257 days, and 597 days ($p<0.0001$). When they combined NSCLC, HNSCC, ovarian the patients with no rash, grade 1 rash and grade 2/3 rash had OS 103 days, 191 days, and 266 days ($p=0.0001$). | |
| Saridaki Z ¹⁹ | Metastatic colorectal cancer | Cetuximab | patients with no rash, grade 1 rash and grade 2 rash had time to progression of 2.3 mo, 4.5 mo, 7.5 mo ($p<0.0001$) and OS of 4.9 mo, 13.2 mo, 24.1 mo ($p<0.0001$). | |
| Stintzing S ²⁰ | Metastatic colorectal cancer | Cetuximab | Patients with grade 2/3 vs 0/1 had better overall response rate (62% vs. 41%), PFS (7.8 months vs. 5.2 months) and OS (30.3 months vs. 18.0 months). | grade 0-1 was observed in 31%, grade 2-3 in 69 % of patients. First-cycle rash was observed in 66% of patients |

| | | | | |
|--------------------------|-------|-----------|--|---|
| Gatzemeier ²¹ | NSCLC | cetuximab | patients with no rash in 1st cycle vs those with rash in first cycle, progression free survival was 4.3 mo vs 5.4 mo (p=0.0031), and OS was 8.8 mo vs 15 mo (p<0.0001). The benefit was seen in all histologies. | acneiform rash developed in the first cycle (21 days) for 56% of the patients receiving cetuximab |
|--------------------------|-------|-----------|--|---|

Several features make rash attractive for predicting sensitivity to cetuximab in a protocol

- 1) It predicts response to EGFR antagonists reliably, as shown in the above table
- 2) It is common
Of 208 pts receiving cetuximab and RT in the Bonner trial, 127 (61%) had prominent rash while 81 (39%) had no or mild rash
- 3) It happens quickly, so it can be used to make therapeutic decisions
Most often within 2 weeks, per the Bonner trial, as illustrated below:

[figure not shown]

Figure 4: The onset of cetuximab-induced rash following the initiation of first treatment

Why do some get rash and some don't?

Some possible explanations are:

- 1) Is this solely a drug delivery issue i.e., some people get adequate doses of cetuximab to the skin and tumor and therefore, develop the rash and also respond at the primary tumor

site? The EVEREST (Evaluation of various erbitux regimens by means of skin and tumor biopsies) trial took patients with metastatic colorectal cancer who had previously received chemotherapy and gave them 3 weeks of irinotecan + cetuximab (400 mg/m² initial then weekly 250 mg/m²). Those who failed to achieve grade 2+ rash at the standard dose (89 pts) were randomized to standard cetux dose vs. dose escalation cetux (up to 500 mg/m²). Dose escalation did increase grade 2+ rash (59% vs. 38%) and overall response rate (30% vs. 16%) but not PFS (4.8 vs. 3.9 mo) or OS (8.6 vs. 10 mo). The response rate benefit was predictably related to Kras: in wild type KRAS the higher dose improved RR (43% vs. 30%), but had no effect on mutant KRAS (0% vs. 0%).²² Therefore, dose escalation may increase skin rash and response, but no evidence that it will improve PFS or OS. And even in the dose escalated patients, there were still about 40% who failed to develop significant skin rash.

- 2) Is this an immune response issue? Several authors have demonstrated that cetuximab does rely somewhat on antibody dependent cell cytotoxicity for tumor killing. Zhen et al demonstrated that a cetuximab molecule with just the F(ab')2 component (missing the Fc component) had less cell killing than an intact antibody.²³ Andres Lopez-Albaitero demonstrated that Cetuximab and panitumumab apparently cannot cause antibody dependent cell cytotoxicity without the presence of peripheral blood lymphocytes.²⁴
- 3) Is there some common susceptibility to EGFR antagonists between the skin and carcinomas? Please see section 2.1 above under *Determining who will respond to cetuximab*.
- 4) Does it have to do with pattern of her family dimerization? Laux et al found that the predominant type of Her family dimerization in the skin was EGFR homodimerization in 16 patients with breast cancer. They note that EGFR-her2 heterodimerization is rare in the skin, and the reason why EGFR inhibitors cause rash and her2 inhibitors do not.²⁵

How rash is used in this protocol. The essence of this protocol is to give a course of neoadjuvant cetuximab (in the Bonner trial they gave 1 week of cetuximab loading dose prior to cetuximab EBRT whereas in this protocol we give 3 weeks of neoadjuvant cetuximab prior to EBRT), select out the patients who develop cetuximab associated folliculitis (section 7.2.3.1) or at least a partial response by RECIST 1.1 CT criteria, and treat those selected patients with concurrent cetuximab EBRT. Those patients who have neither a cetuximab related folliculitis or CT response will be treated with the standard cisplatin EBRT.

We anticipate that most of the patients who qualify to receive cetuximab EBRT will do so because of the folliculitis criteria. The CT partial response criteria by RECIST 1.1 is included in case of the anticipated rare case where there is a patient who does not develop folliculitis but does respond radiographically to neoadjuvant cetuximab. This patient should clearly go on the cetuximab EBRT arm and this criteria is meant to include this patient, though we anticipate that this will occur very rarely.

[figure not shown]
Why get a repeat biopsy after neoadjuvant cetuximab? This protocol involves a re-biopsy after the 3 weeks of neoadjuvant cetuximab. Recently, data has revealed that H&N SCC sometimes uses alternate molecular pathways as escape mechanisms. One possible pathway is the IGF-1R pathway. IGF-1R is widely present in HNSCC, and Barnes found that stimulation of head and neck cancer cells with either IGF or EGF resulted in IGF-IR and EGFR heterodimerization, but only IGF caused activating phosphorylation of both receptors. Combined treatment with A12 (IGF-1R antagonist) and cetuximab was more effective at reducing cell proliferation and migration than either agent alone.²⁶ There is evidence that EGFR and IGF-1R interact on multiple levels, either through a direct association between the two receptors, by mediating the availability of each other's ligands, or indirectly, via common interaction partners such as G protein coupled receptors (GPCR) or downstream signaling molecules. This multi-layered cross-talk may be involved in induction of resistance to targeted therapies.²⁷ Morgillo found that in NSCLC cell lines, that treatment with erlotinib increased the levels of EGFR/IGF-IR heterodimer localized on cell membrane, activated IGF-IR and its downstream signaling mediators.²⁸ With regard to radiation therapy, Ang et.al., found that in mice bearing HNSCC xenografts, that the best tumor growth delay was achieved when ganitumab (IGF-1R inhibitor) and panitumumab (EGFR inhibitor) were given concurrently with radiation. Interestingly, when the ganitumab was given with the radiation, followed by panitumumab, the tumor killing was not as effective as when the agents were given together with radiation, or when panitumumab was given with radiation, followed by ganitumab.²⁹

[figure not shown]
This platform, (bx before and after neoadjuvant cetuximab) is a unique opportunity to look for changes in protein or mRNA production in response to EGFR inhibitor. There are a number of protocols that have combined EGFR inhibitor with neoadjuvant chemotherapy such as TPF; however, molecular analysis of bx done after such a cocktail is difficult to interpret as there are multiple agents involved. No one to our knowledge has had such a platform to assess tumor escape pathways to just EGFR inhibitor *in vivo*. This may reveal IGF-1R as a significant escape pathway, or perhaps other, alternate pathways.

3. Participating Institutions

Clinical activities will take place at Rutgers New Jersey Medical School in Newark and Rutgers Cancer Institute of New Jersey. Some molecular correlative studies will be performed at Rutgers Cancer Institute of New Jersey.

4. Experimental Design and Methods

*if tooth extraction is necessary, should be extracted during neoadjuvant cetuximab or before so as not to delay radiation therapy. All patients will be encouraged to have PEG placed prior to radiation or early on in the radiation course but failure to do so will not exclude them from the protocol.

